### 10.2.3. Preparation for Administration

If the silicone-free disposable syringe is dropped or becomes contaminated, use a new silicone-free disposable syringe from inventory.

1. Calculate the number of NULOJIX® vials required to provide the total infusion dose. Each vial contains 250 mg of belatacept lyophilized powder.
2. Reconstitute the contents of each vial of NULOJIX® with 10.5 mL of a suitable diluent using the silicone-free disposable syringe provided with each vial and an 18- to 21-gauge needle.

Suitable diluents include: sterile water for injection (SWFI), 0.9% sodium chloride (NS), or 5% dextrose in water (D5W). Note: If the NULOJIX® powder is accidentally reconstituted using a different syringe than the one provided, the solution may develop a few translucent particles. Discard any solutions prepared using siliconized syringes.

3. To reconstitute the NULOJIX® powder, remove the flip-top from the vial and wipe the top with an alcohol swab. Insert the syringe needle into the vial through the center of the rubber stopper and direct the stream of diluent (10.5 mL of SWFI, NS, or D5W) to the glass wall of the vial.
4. To minimize foam formation, rotate the vial and invert with gentle swirling until the contents are completely dissolved. Avoid prolonged or vigorous agitation. Do not shake.
5. The reconstituted solution contains a belatacept concentration of 25 mg/mL and should be clear to slightly opalescent and colorless to pale yellow. Do not use if opaque particles, discoloration, or other foreign particles are present.
6. Calculate the total volume of the reconstituted 25 mg/mL NULOJIX® solution required to provide the total infusion dose.  $\text{Volume of 25 mg/mL NULOJIX}^{\text{®}} \text{ solution (in mL)} = \text{Prescribed Dose (in mg)} \div 25 \text{ mg/mL}$
7. Prior to intravenous infusion, the required volume of the reconstituted NULOJIX® solution must be further diluted with a suitable infusion fluid (NS or D5W). NULOJIX® reconstituted with:
  - SWFI should be further diluted with either NS or D5W
  - NS should be further diluted with NS
  - D5W should be further diluted with D5W
8. From the appropriate size infusion bag or bottle, withdraw a volume of infusion fluid that is equal to the volume of the reconstituted NULOJIX® solution required to provide the prescribed dose. With the same silicone-free disposable syringe used for reconstitution,

withdraw the required amount of belatacept solution from the vial, inject it into the infusion bag or bottle, and gently rotate the infusion bag or bottle to ensure mixing.

The final belatacept concentration in the infusion bag or bottle should range from 2 mg/mL to 10 mg/mL. Typically, an infusion volume of 100 mL will be appropriate for most patients and doses, but total infusion volumes ranging from 50 mL to 250 mL may be used. Any unused solution remaining in the vials must be discarded.

9. Prior to administration, the NULOJIX® infusion should be inspected visually for particulate matter and discoloration. Discard the infusion if any particulate matter or discoloration is observed.
10. The entire NULOJIX® infusion should be administered over a period of 30 minutes and must be administered with an infusion set and a sterile, non-pyrogenic, low-protein-binding filter (with a pore size of 0.2-1.2 µm).
  - The reconstituted solution should be transferred from the vial to the infusion bag or bottle immediately. The NULOJIX® infusion must be completed within 24 hours of reconstitution of the NULOJIX® lyophilized powder. If not used immediately, the infusion solution may be stored under refrigeration conditions: 2°-8°C (36°-46°F) and protected from light for up to 24 hours (a maximum of 4 hours of the total 24 hours can be at room temperature: 20°-25°C [68°-77°F] and room light).
  - Infuse NULOJIX® in a separate line from other concomitantly infused agents. NULOJIX® should not be infused concomitantly in the same intravenous line with other agents. No physical or biochemical compatibility studies have been conducted to evaluate the coadministration of NULOJIX® with other agents.
  - VIB4920 should be administered prior to belatacept. Timings of administration of each drug should be recorded.

### **10.3. Thymoglobulin**

#### **10.3.1. Supply**

Thymoglobulin will be dispensed by the site's hospital pharmacy. Thymoglobulin is supplied as a single-use clear glass 10 mL vial containing 25 mg of lyophilized (solid) Thymoglobulin. Each carton contains one Thymoglobulin vial (NDC 58468-0080-1) (Food and Drug Administration 2017).

#### **10.3.2. Storage/Handling**

- Store in refrigerator at 2°C to 8°C (36°F to 46°F).
- Protect from light.
- Do not freeze.
- Do not use after the expiration date indicated on the label.
- Reconstituted Thymoglobulin is physically and chemically stable for up to 24 hours at room temperature; however, room temperature storage is not recommended. As

Thymoglobulin contains no preservatives, reconstituted product should be used immediately.

- Infusion solutions of Thymoglobulin must be used immediately.
- Any unused drug remaining after infusion must be discarded.

### **10.3.3. Instructions for Dilution and Administration**

#### **10.3.3.1. Reconstitution**

After calculating the number of vials needed, using aseptic technique, reconstitute each vial of Thymoglobulin with 5 mL of SWFI, USP.

1. Allow Thymoglobulin vials to reach room temperature before reconstituting the lyophilized product.
2. Aseptically remove caps to expose rubber stoppers.
3. Clean stoppers with germicidal or alcohol swab.
4. Aseptically reconstitute each vial of Thymoglobulin lyophilized powder with the 5 mL of SWFI.
5. Rotate vial gently until powder is completely dissolved. Each reconstituted vial contains 25 mg or 5 mg/mL of Thymoglobulin.
6. Inspect solution for particulate matter after reconstitution. Should some particulate matter remain, continue to gently rotate the vial until no particulate matter is visible. If particulate matter persists, discard this vial.

#### **10.3.3.2. Dilution**

1. Transfer the contents of the calculated number of Thymoglobulin vials into the bag of infusion solution (saline or dextrose). Recommended volume: per one vial of Thymoglobulin use 50 mL of infusion solution (total volume usually between 50 to 500 mL)
2. Mix the solution by inverting the bag gently only once or twice.

#### **10.3.3.3. Infusion**

Administer Thymoglobulin under strict medical supervision in a hospital setting, and carefully monitor patients during the infusion.

Thymoglobulin is less likely to produce side effects when administered at the recommended flow rate.

1. Follow the manufacturer's instructions for the infusion administration set. Infuse through a 0.22 micrometer filter into a high-flow vein.
2. Set the flow rate to deliver the dose over a minimum of 6 hours for the single dose.

## **10.4. Corticosteroids**

Corticosteroids (methylprednisolone and prednisone) will be dispensed by the hospital pharmacy and administered in the protocol-specified dose regimen.

## **11. STUDY ASSESSMENTS AND PROCEDURES**

### **11.1.1. Informed Consent**

All candidates for enrollment or legally authorized representative will sign an ICF prior to any screening activities. Informed consent must be obtained by the principal investigator or a designee, such as a sub-investigator, with IRB-approved qualifications.

Each patient must be given the opportunity to ask questions and to understand the details of study participation.

The consent process must be recorded in the subject's source documents and evidenced by the patient signing the ICF.

After signing the ICF, each subject will be assigned an identification number that will be used on all subject documentation. Numbers will be assigned in ascending sequential order. This number will also correspond to the subject number entered on test materials.

### **11.1.2. Demographic/Medical History**

Demographic information to be collected includes date of birth, sex, race and ethnicity.

Medical history information to be collected includes all ongoing conditions and relevant/significant medical history (including all major hospitalizations and surgeries), as determined by the Investigator.

### **11.1.3. Background (donor and recipient)**

The following background information should be collected from donors: sex, race, ethnicity, transplant donor type (living related, living unrelated, deceased heart beating, deceased non-heart beating).

The following recipient background information should be collected: end-stage renal disease leading to transplantation, current dialysis (none, hemodialysis, peritoneal dialysis) and dialysis start date, highest Panel Reactive Antibody (PRA) test, most recent PRA and HLA type.

### **11.1.4. Vital Signs**

Vital signs including systolic and diastolic blood pressure (mmHg), pulse rate (beats/min), respiratory rate (RR) (breaths/min), body temperature (°C) and body weight (kg) will be measured using clinically acceptable methods and devices as defined in the schedule of events and IP Administration manual.

### **11.1.5. Physical Examination**

A complete physical examination will be completed at screening, while symptom-directed physical examinations will be performed thereafter, as specified in the Schedule of Assessments.

A complete physical examination will include the examination of the following body systems: general appearance, skin, HEENT (head, ears, eyes, nose, throat), cardiovascular, pulmonary, abdomen, neurological, lymph nodes, spine and extremities (skeletal). As part of the complete physical examination, a clinical assessment will be performed and will include the evaluation of the subject for clinical signs of infection, allograft rejection, AEs, and change in renal function. Any abnormalities will be recorded on the Case Report Form (CRF). At screening, abnormalities will be recorded on the medical history eCRF page. Clinically significant changes from baseline physical examination that are detected during follow-up will be recorded as an AE on the appropriate eCRF pages.

#### **11.1.6. Electrocardiogram (ECG)**

A 12-lead electrocardiogram (ECG) will be performed. Each ECG will include ventricular heart rate and intervals (PR, QRS, QT, QTc). The PI will be responsible for providing an interpretation of the ECGs in terms of clinical significance to the subject (i.e., normal, abnormal but not clinically significant, abnormal and clinically significant.). Any abnormalities and clinical significance will be entered on the eCRF.

#### **11.1.7. Laboratory Assessments**

Blood and urine samples will be collected for laboratory safety tests as specified in the Schedule of Assessments. Laboratory testing is described below. For further details regarding laboratory assessments see the Study Laboratory Manual.

##### **11.1.7.1 Hematology**

The hematology panel will include a complete blood count, with differential (including basophils, eosinophils, lymphocytes, monocytes, and neutrophils), hemoglobin, hematocrit, platelets and white blood cell count.

##### **11.1.7.2 Blood Chemistry**

Chemistry and Renal Profile:

- Creatinine, blood urea nitrogen, fasting glucose, total protein and electrolytes (including sodium, potassium, chloride, calcium, bicarbonate, and phosphorus)

Hepatic Profile:

- Albumin, total bilirubin, indirect bilirubin, AST, ALT, alkaline phosphatase (ALP), and gamma glutamyl transferase.

##### **11.1.7.3 Immunoglobulins**

- Total immunoglobulins, IgA, IgG and IgM.

##### **11.1.7.4 Coagulation Parameters**

Prothrombin time and partial thromboplastin time will be assessed.

#### 11.1.7.5. Urinalysis

The urinalysis will include protein, glucose, blood, ketones, leukocytes, and pH by dipstick analysis. Microscopy (crystals, casts, white blood cells, red blood cells) will also be performed if any abnormalities are observed.

#### 11.1.8. Viral Serology

Serological tests for exposure to CMV, EBV, hepatitis C virus (HCV), HBsAg and HIV will be performed for recipient and donor at screening, if not conducted within the previous 12 months. Additionally, viral monitoring for BK polyoma virus, CMV and EBV will be conducted throughout the study, as specified in the Schedule of Assessments ([Table 3](#) and

[Table 4](#)).

#### 11.1.9. Pregnancy Screen

Serum human chorionic gonadotrophin beta (hCG $\beta$ ) pregnancy test(s) will be completed for all females of childbearing potential during the screening period (before Day 0). Females screened within 1 week prior to Day 0 will not need to repeat the pregnancy test as part of the reconfirmation of eligibility. In the post-transplant period, serum or urine hCG $\beta$  pregnancy tests (at the investigator's discretion) will be performed as specified in the Schedule of Assessments ([Table 3](#) and

[Table 4](#)).

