Subjects with evidence of renal allograft dysfunction (rising serum creatinine not attributable to technical complications) and/or evidence of cell-mediated or antibody mediated rejection on biopsy will be treated with additional immunosuppression, as clinically indicated and according to standard care at each participating clinical site. Whether to continue VIB4920+belatacept will be determined based on the histologic grade of the rejection and the clinical response to immunosuppressive therapy, as defined below.

Written informed consent and any locally required authorization (e.g., data privacy) will be obtained from the subject prior to performing any protocol-related procedures, including screening evaluations. Patients may be screened between Day -28 and Day -1 prior to transplantation, with eligibility reconfirmed on Day 0 prior to induction of anesthesia for transplant surgery and prior to administration of Thymoglobulin or methylprednisolone. Subjects will be admitted to the transplant center for administration of VIB4920 and belatacept, observation and assessment of safety/tolerability and may be discharged after administration of belatacept+VIB4920 on Day 3 or 4 (at the discretion of the investigator) following completion of all scheduled Visit 4 assessments. Subjects will return to the study center for safety monitoring on Day 7 and for administration of study medication(s) and safety monitoring on Week 2; then every 2 weeks for 5 visits (at the end of Weeks 4, 6, 8, 10 and 12), and then monthly for 9 visits (at the end of Weeks 16, 20, 24, 28, 32, 36, 40, 44 and 48). All subjects will be followed on study through Week 48 for acute rejection, graft survival and patient survival. Subjects who prematurely discontinue treatment with VIB4920 and/or belatacept will undergo an End-of-Treatment visit at time of discontinuation and follow Schedule of Assessments through Week 48 and at least three months after last dose with VIB4920 and/or belatacept completing the study with End of Study visit. Subjects who are unwilling to comply with study schedule after early discontinuation of treatment should undergo End-of-Treatment/End-of-Study visit at time of discontinuation and undergo complete safety follow up at 4, 8, and 12-weeks after end treatment visit. Subjects who wish to prematurely discontinue study participation should be asked to undergo an End-of-Study visit assessment before withdrawing consent.

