**Table 3: Schedule of Assessments – Treatment period (Day 0 to Week 24)**

Study Period	Treatment Period (Day 0 to Week 24)												
Visit Number	V2	V3	V4	V5	V6	V7	V8	V9	V10	V11	V12	V13	V14
Procedure a/ Study Day or Week	Day 0	Day 1	Day 3 or 4	Day 7	Week 2 ± 1 day	Week 4 ± 2 days	Week 6 ± 2 days	Week 8 ± 2 days	Week 10 ± 2 days	Week 12 + 2 days	Week 16 ± 3 days	Week 20 ± 3 days	Week 24 + 3 days
Inclusion/exclusion criteria	X b												
Thymoglobulin	Day 0 to Day 3												
Corticosteroids	Day 0 to Day 28												
VIB4920 administration c		X	X e		X	X	X	X	X	X	X	X	X
Belatacept administration		X d	X e		X	X		X		X	X	X	X
Vital signs f	X	X	X	X	X	X	X	X	X	X	X	X	X
Physical examination g	X					X				X			X
12-lead ECG	X	X				X				X			X
Hematology h	X	X	X	X	X	X	X	X	X	X	X	X	X
Blood chemistry i	X	X	X	X	X	X	X	X	X	X	X	X	X
Immunoglobulins j	X					X				X			X
Coagulation parameters k	X	X			X	X		X		X	X	X	X
Pregnancy test l	X					X		X		X	X	X	X
Urinalysis m		X				X		X		X			X
Spot UPCR n		X		X	X	X		X		X	X	X	X
BK polyoma viral load		X			X	X	X	X	X	X	X	X	X
CMV, EBV viral load		X				X		X		X			X
CCI [REDACTED]	X					X				X			X
CCI [REDACTED]	X				X	X				X			X
CCI [REDACTED]	X					X				X			X
Pharmacokinetics		X q	X q	X	X	X		X	X q	X	X		X
Immunogenicity r		X				X				X			X
CCI [REDACTED]	X	X	X	X	X	X		X	X	X	X		X
CCI [REDACTED]	X					X			X	X			X

CCI [REDACTED]	X					X				X			X
CCI [REDACTED]	X		X		X	X		X		X			X
Surveillance biopsy v	X												X
Prior and concomitant meds w	X	X	X	X	X	X	X	X	X	X	X	X	X
Adverse events x	X	X	X	X	X	X	X	X	X	X	X	X	X

- a Unless otherwise noted, blood collections to be drawn prior to therapeutic administration. Site staff will administer all study medications intravenously at the study center, except for prednisone (which will be self-administered by the subject at Day 4 through Day 28).
- b Subject’s eligibility to be reconfirmed prior to administration of Thymoglobulin and induction of anesthesia for transplant surgery on Day 0.
- c Each subject must receive the entire volume of investigational product solution in the IV bag over 90 minutes (approximately 2.8 mL/min). VIB4920 should be administered prior to belatacept.

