- d First dose of belatacept on Day 1 to be given no sooner than 12 hours after the end of Thymoglobulin infusion.
- e Second dose of belatacept+VIB4920 may be administered on Day 3 (instead of Day 4) to facilitate early hospital discharge, at investigator’s discretion.
- f Vital signs (BP, heart [pulse] rate, respiratory rate, and body temperature) will be obtained prior to the start of each VIB4920 infusion.
- g A complete physical examination will include general appearance, skin, HEENT (head, ears, eyes, nose, throat), cardiovascular, pulmonary, abdomen, neurological, lymph nodes, spine and extremities (skeletal). As part of the physical examination, a clinical assessment will be performed and will include the evaluation of the subject for clinical signs of infection, allograft rejection, AEs, and change in renal function. Any abnormalities will be recorded on the Case Report Form (CRF). Clinically significant changes from baseline physical examination that are detected during follow-up will be recorded as an AE on the appropriate eCRF pages.
- h Complete blood count, with differential (including basophils, eosinophils, lymphocytes, monocytes and neutrophils, hemoglobin, hematocrit, platelets and white blood cell count.
- i Chemistry and renal profile (creatinine, blood urea nitrogen, fasting glucose, total protein and electrolytes [including sodium, potassium, chloride, calcium, bicarbonate, and phosphorus]). Hepatic profile will include albumin, total bilirubin, indirect bilirubin, AST, ALT, ALP and gamma glutamyl transferase.
- j Total immunoglobulins, IgA, IgG and IgM.
- k Coagulation parameters will include prothrombin time and partial thromboplastin time.
- l Serum or urine hCGβ (females of childbearing potential only).
- m Protein, glucose, blood, ketones, leukocytes, and pH by dipstick analysis. Microscopy (crystals, casts, white blood cells, red blood cells) will be performed if any abnormalities are observed.
- n UPCR - quantitation of proteinuria and urine protein:creatinine ratio by spot urine.
- o Blood CCI [REDACTED].
- p Blood CCI [REDACTED].
- q At V3, V4, V10, plasma samples for PK of VIB4920 to be taken predose and within 10 minutes after the end of infusion.
- r Plasma samples for immunogenicity to be taken prior to administration of drug.

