## **8. SELECTION AND WITHDRAWAL OF SUBJECTS**

### **8.1. Subject Inclusion Criteria**

Subjects must meet all of the following criteria to be eligible for study inclusion:

1. Written informed consent and any locally required authorization (e.g., data privacy) obtained from the patient prior to performing any protocol-related procedures, including screening evaluations.
2. Male or female recipients aged 18-70.
3. Recipients of a first renal transplant from a standard criteria deceased, living unrelated or HLA non-identical living related donor.
4. Recipients who are at low immunologic risk:
  - a. No DSA, and
  - b. Negative cross-match testing (by T- and B- cell flow or by virtual cross-match).
5. Recipients with up to date vaccination as per local immunization schedules.
6. A female subject is eligible if she is:
  - a. Not pregnant or nursing.
  - b. Of non-childbearing potential (i.e., post-menopausal defined as having been amenorrheic for at least 1 year prior to screening, or has had a bilateral tubal ligation at least 6 months prior to screening, or has had a bilateral oophorectomy or hysterectomy).
  - c. Of childbearing potential, must have a negative serum pregnancy test within 48 hours prior to surgery and be using an effective method of contraception (per site specific recommendations) which must be continued for at least 6 months after the final dose of investigational product.
7. Nonsterilized male subjects who are sexually active with a female partner of childbearing potential must use a condom with spermicide from Day 0 through to the end of the study and must agree to continue using such precautions for at least 6 months after the final dose of investigational product.

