**Table 6: Estimate of Total Blood Volume to be collected per study visit**

Study Period	Approximate Volume (mL)
Screening Period	42
Day 0	64
Day 1	43
Day 3 or 4	31
Day 7	23
Week 2 ± 1 day	40
Week 4 ± 2 days	82
Week 6 ± 2 days	12
Week 8 ± 2 days	45
Week 10 ± 2 days	29
Week 12 + 2 days	82
Week 16 ± 3 days	32
Week 20 ± 3 days	16
Week 24 +3 days	82
Week 28 ± 3 days	32
Week 32 ± 3 days	16
Week 36 ± 3 days	68
Week 40 ± 3 days	32
Week 44 ± 3 days	16
Week 48 +3 days	82
EOT	78
End of Treatment + 4 weeks	14
End of Treatment + 8 weeks	35
End of Treatment + 12 weeks	82
Total	995

The volume of blood was estimated assuming that a serum pregnancy test will be performed. Thus, the volume of blood to be collected may be less for subjects performing urine pregnancy tests.

Total may be less than indicated for subjects with available serological tests for exposure to CMV, EBV, HCV, HBsAg and HIV performed within the 12 months prior to screening and those who prematurely discontinue study treatment.

Total excludes the End-of-Treatment visit.

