3.2 Protocol Deviations

All protocol deviations will be classified as either major protocol deviations or minor protocol deviations. The major protocol deviations are considered as the important protocol deviations, which may significantly impact the completeness, accuracy, and/or reliability of the study data, and may significantly affect a subject's rights, safety, or well-being. All the protocol deviations will be listed, and the major protocol deviation will be summarized. Some classifications of major protocol deviations are listed below.

- Did not meet inclusion criteria or met exclusion criteria.
- Received prohibited concomitant medication.
- Met IP discontinuation criteria but was not discontinued from the IP.
- Serious breach of good clinical practice.

The list may be updated and will be finalized and documented prior to the database lock.

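### The one-week pregnancy-test waiver in Protocol 11.1.9 conflicts with the 48-hour serum test required by inclusion criterion 6c

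*Protocol*

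**What the plan says.** Inclusion criterion 6c, worded alike in the synopsis and Protocol Section 8.1, states that a woman of childbearing potential "must have a negative serum pregnancy test within 48 hours prior to surgery".

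Protocol Section 11.1.9 calls for serum testing during screening and then adds: "Females screened within 1 week prior to Day 0 will not need to repeat the pregnancy test as part of the reconfirmation of eligibility". It gives the investigator a choice of serum or urine only for tests after the transplant.

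On timing, Protocol Section 7.1 sets the screening window at Day -28 to Day -1 and places a second check just before the operation: "with eligibility reconfirmed on Day 0 prior to induction of anesthesia for transplant surgery". Footnote b of Table 3 likewise requires "eligibility to be reconfirmed prior to administration of Thymoglobulin and induction of anesthesia for transplant surgery on Day 0".

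Table 3 also has a pregnancy-test row, separate from the eligibility row, marked at Day 0 and next at Week 4. Its footnote l accepts serum or urine for the whole row and contains no waiver.

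SAP Section 3.2 lists among its major protocol deviations: "Did not meet inclusion criteria or met exclusion criteria".

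**The concern.** Both rules are current text, both concern eligibility, and they set different limits on how old the last pregnancy test may be. Section 11.1.9 is the specific procedural instruction on pregnancy screening, so site staff could follow it in good faith and enter a woman who has no qualifying test under 6c. Failing 6c here means that the required recent serum result is absent, not that she is known to be pregnant.

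The stake is safety. A pregnancy that became detectable only after a test done 3 to 7 days before surgery could go unnoticed while T-cell-depleting induction, VIB4920, belatacept and corticosteroids are given. The protocol itself treats pregnancy as an exclusion (criterion 29) and as a reason for permanent discontinuation of study drug (Section 8.3). A smaller cost is that a site that followed 11.1.9 would generate a major deviation under SAP 3.2.

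**Working it through.** The plan gives no figure to reproduce. The check is a comparison of the rules, with simple counts from Tables 3 and 5.

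**Rules side by side**

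| Source | Oldest acceptable test | Specimen | Anchor |
|---|---|---|---|
| Inclusion 6c | 48 h | serum | surgery |
| Section 11.1.9 waiver | 1 week = 7 × 24 = 168 h | serum (screening test) | Day 0 |
| Table 3, Day 0 column, footnote l | test on the day | serum or urine | Day 0 |

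**Size of the gap.** 168 h − 48 h = 120 h, or 5 days. The waiver window is 168 / 48 = 3.5 times the 6c window.

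- Test no more than 48 h before surgery: 6c is met and the waiver does no harm.
- Test more than 48 h and up to about 168 h before surgery: 11.1.9 excuses a repeat, and 6c is unmet without one.
- Screening more than a week before Day 0: the waiver does not apply.

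Whatever the waiver adds to 6c therefore consists of tests that 6c rejects. The 120 h is approximate. One rule counts from a calendar day and the other from the time of surgery, and 11.1.9 refers to when a woman was screened, which need not be the date of her test.

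**Does the Day 0 test in Table 3 close the gap?** Not reliably, for three reasons.

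1. Footnote l allows urine at Day 0, and a urine result does not meet a serum requirement. This also differs from 11.1.9, which offers that choice only after transplant.
2. Eligibility is reconfirmed on Day 0, so the waiver can be read as cancelling the Day 0 test.
3. Footnote a of Table 3 places blood draws before dosing. It says nothing about when the result must be available, and it does not cover urine.

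**Exposure before the next test if the Day 0 test is taken as waived** (Tables 3 and 5; next test at Week 4, before that visit's dosing)

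- Thymoglobulin on Days 0, 1, 2 and 3: 4 doses, 4 × 1.5 = 6 mg/kg.
- VIB4920 on Day 1, Day 3 or 4, and Week 2: 3 doses, 3 × 1500 = 4500 mg.
- Belatacept on the same three occasions: 3 doses, 3 × 10 = 30 mg/kg.
- Longest interval between tests: 7 + 28 = 35 days, or 37 with the 2-day visit window. With 6c met it is 2 + 28 = 30 days, or 32.

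**Effect on the analysis.** The efficacy evaluable set (Protocol 14.1.1.2, SAP 3.3.2) is defined by receipt of the revised Thymoglobulin and steroid regimen and any dose of investigational product. A deviation on 6c removes no one, so the primary analysis is unchanged.

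**The case against.** The strongest reply is that 6c still binds. Section 8.1 requires every inclusion criterion to be met. Section 11.1.9 is a procedures paragraph that excuses a repeat test but nowhere says that an older test satisfies 6c. A site can comply with both by testing within 48 hours. On this view there is a stricter rule that plainly governs, and the fault is one of wording. SAP 3.2 supports this, because it treats an unmet inclusion criterion as a deviation to be summarised.

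The exposure scenario also needs several things to go wrong together. The site must overlook 6c, read 11.1.9 as cancelling the Day 0 test in Table 3, and enrol a woman whose pregnancy became detectable only after the screening test. Required contraception and exclusion 29 lower the chance further, and nothing shows that a Day 0 urine test would miss a pregnancy.

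Much of this stands. The dose counts describe the least favourable reading, and 120 hours should be taken as approximate. The conflict remains all the same. The protocol does not say which rule prevails, and an explicit exemption in the section devoted to pregnancy testing invites use. If 6c always governs, the one-week limit has no function and should be removed.

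**Conclusion.** The concern holds. The two rules are inconsistent for any serum test more than 48 hours and up to about one week old at surgery, a gap of roughly 120 hours (about Day -7 to Day -3). A woman in that gap could be cleared under 11.1.9 without meeting 6c, and the Day 0 entry in Table 3 does not settle the matter.

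The textual conflict is certain. The safety consequence is conditional: exposure to 4 Thymoglobulin, 3 VIB4920 and 3 belatacept doses before the next test assumes that the Day 0 test is treated as waived. The number of women affected cannot be estimated and could be zero. The documents give neither the number of women of childbearing potential among the roughly 20 subjects nor the timing of their tests. This is an eligibility and safety correction that should be made; it has no bearing on the sample size or the primary analysis.

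**What to change.** Bring two places into line with inclusion 6c in one amendment.

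1. **Section 11.1.9:** limit the waiver to women who already have a negative serum hCG within 48 hours before surgery.
2. **Table 3, footnote l:** make the Day 0 test serum, with the result available before induction of anesthesia and before Thymoglobulin, unless a negative serum test within 48 hours before surgery already exists. Allow serum or urine from Week 4 onward.

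The cost is the wording change and at most one extra serum hCG in a few subjects. The planned blood volume does not rise. The note to Table 6 says "The volume of blood was estimated assuming that a serum pregnancy test will be performed", so the 64 mL planned for Day 0 already allows for it.
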